
### **Approach**

**The proposed project determining the clinical effectiveness of AE in facilitating motor recovery and determining the cost-effective strategy could fundamentally alter current rehabilitation approaches and drive the adoption of AE into stroke rehabilitation.**

**Experimental Overview:** A prospective, single-center, parallel group, rater-blind clinical trial is proposed. A schematic depicting workflow and outcomes is provided in Figure 2. A total of 60 individuals with chronic

stroke (>6 months) will be randomized to one of two time-matched groups: 1) AE and RTP or 2) RTP only. All groups receive an identical dose of contact time (36 hours) over a course of 8 weeks (3X per week). Upper extremity motor outcomes (Aim 1) will be collected at baseline, mid-treatment, end of treatment (EOT), and EOT+4 weeks. Data concerning participant demographics, social determinants, and intervention resource utilization (including personnel) will be collected during the clinical trial and at 6-months (primary outcome on full data set, Aim 2) and 12-months follow-up (secondary outcome on subset of sample, Aim 2).

**The following elements of our experimental design ensure scientific rigor:** 1) Randomization stratified according to baseline function and age; 2) Blinding of the rater; 3) Utilization of a time-matched control group; 4) Sample size justified to demonstrate group differences based on preliminary studies; and 5) Sound statistical analysis plan. An intent-to-treat approach will be used to address any missing data; to date <1% of data in our preliminary studies are missing.

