**Cost-Effectiveness Analysis Variables (Aim 2):** Extensive participant demographics including age, gender, education, employment, support system, and social responsibilities will be collected at each time point in addition to the SIS and PROMIS 29. These measures will ensure the accurate calculation of quality indices and indirect costs. Direct medical costs including personnel time, equipment, and additional resources and consumables associated with each intervention will be collected throughout the intervention period. Labor prices will be sourced from the Bureau of Labor and Statistics using US averages. All costs will be adjusted to the same base year using the Medical Component of the Consumer Price Index. Discounting will be applied in line with the Recommendations of the 2nd Panel on Cost-Effectiveness in Health and Medicine.

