### **Data analysis**

**Consideration of Relevant Biological and Sociological Variables:** Participants in both groups will be compared on potentially confounding baseline variables (age, gender, socio-economic status, education, fitness, co-morbidities, degree of hemiplegia, location/type of stroke, side of lesion) to assess the extent of any imbalances across groups. Baseline variables in which there is a clinically important difference between groups may be included as covariates. Participants will also be compared using participation and adherence metrics. While recent evidence has shown that genetic polymorphisms may influence motor recovery following stroke, it is beyond the scope of this project due to cost and lack of expertise to consider these as covariates.

**Analysis of Motor Outcomes (Aim 1):** Motor outcomes for each group will be compared at baseline, mid-treatment, EOT, and EOT+4. The group effect on ARAT, FMA, and WMFT will be estimated using separate linear mixed effects models with a random effect for subject, fixed effects for group, examination time, and baseline value of the outcome. An appropriate covariance structure (e.g.: unstructured, compound symmetric, autoregressive) will be used as determined using Akaike's information criterion. The effects of group, time, and the group-by-time interaction will be assessed for each outcome. To adjust for multiple comparisons, the family-wise error rate will be controlled via Bonferroni-type adjustment required for multiple comparisons. Tukey's and other post-hoc comparisons will be used to explore pairwise differences in main effects of group membership. To further investigate the effect of the intervention group assignment on the various sub-scales of the ARAT, a multivariate analysis of variance will be used along with a separate principle component analysis to study if further dimension reduction is possible in using these two tests in the study. Transformations of the data will be made to achieve normality or other model assumptions. The overall alpha level will be set at 0.05.

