**Bimanual dexterity data:** All force and torque data will be filtered with a phase-symmetric low-pass filter using Woltring's algorithm with existing Matlab programs. The primary kinetic and kinematic outcomes will be: coordination of grip-load coupling, time delay between grasping force initiation for each limb, overall time to task completion and rate of grip force production for each limb.

**Cost-Effectiveness Analysis (Aim 2):** A decision analytic model using a systematic, quantitative approach using Treeage Pro® will be developed comparing AE+RTP and UE RTP only. All possible outcomes will be incorporated into the model. A hospital/payer perspective will be adopted and include all relevant costs and outcomes. All outcome probabilities used in the model will be determined from the clinical trial's data collection at the 6 time points. As part of my training, I will learn cost-effectiveness methodologies, including approaches to analyze variability and uncertainty in the model and the population, and methods to evaluate model generalizability (sensitivity analysis) in accordance with current recommendations. For this analysis, a cost effectiveness summary will be produced, including the costs and effects of each intervention, the cost-effectiveness ratio of the interventions, and the incremental cost-effectiveness ratio between the interventions from two perspectives: healthcare sector and society. Deterministic and probabilistic sensitivity analyses will be used to evaluate result uncertainty attributable to the model and population variability. Sensitivity analyses will be summarized to show that the optimal strategy is the choice strategy in 'what' percentage of time and for 'what' variable values and be reported as a cost-effectiveness acceptability curve.

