### **Power and Sample Size Justification:**

The power and sample size calculation is based on FMA scores from our R03 study. A minimal clinically important difference (MCID) range of 4.25-7.25 points has been reported for the FMA with baseline subject standard deviation of 5.7 – 6.3 points. To be conservative, we have assumed the MCID to be 4.25 for the purposes of our power calculations. Based on results from our R03 which included 3 intervention groups, the forced AE+RTP group, voluntary AE+RTP group, and RTP only groups improved on the FMA by a mean of 12.33(4.13), 4.83(4.91), and 4.4(4.87), respectively. In the sample size and power computation, it is assumed that there is an increase of 2\*MCID for the AE+RTP group and 1\*MCID for the RTP only group, along with

statistically significant differences between the groups at EOT. Further, it is assumed that subject SD will remain ~10 points within the group. Based on these assumptions, with n=30 in each of the intervention groups, we will have a .87 power at the 0.05 significance level to detect pairwise group differences equivalent to an effect size of .4. All computations were completed using the PASS 13 program (East Kaysville, Utah).

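### Baseline adjustment is prespecified for the motor outcomes but not for the QALYs behind the Aim 2 primary ICER, although baseline SIS and PROMIS 29 will be available

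*Combined protocol and SAP*

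**What the plan says.** - **Aim 2, Outcomes.** The primary outcome is the ICER in dollars and QALYs at six months, with a 12-month ICER on a subset. Quality weights come from the SIS and PROMIS 29.
- **Data Variables, Cost-Effectiveness Analysis Variables.** Demographics "will be collected at each time point in addition to the SIS" and PROMIS 29. The cost-effectiveness paragraph of Data analysis counts six time points. That fits the four motor visits (baseline, mid-treatment, end of treatment, four weeks later) plus six and 12 months, so a baseline score is implied.
- **Data analysis, Cost-Effectiveness Analysis (Aim 2).** "All outcome probabilities used in the model will be determined from the clinical" trial. Deterministic and probabilistic sensitivity analyses and an acceptability curve follow. How utilities or QALYs are calculated or compared is not stated, and baseline utility is not mentioned.
- **Data analysis, Analysis of Motor Outcomes (Aim 1).** The mixed models for ARAT, FMA and WMFT have "fixed effects for group, examination time, and baseline value of the outcome".
- **Data analysis, Consideration of Relevant Biological and Sociological Variables.** Groups are compared on a list of baseline variables, and those with a clinically important difference may become covariates. The list does not contain quality of life, SIS or PROMIS 29.
- **Approach.** "A total of 60 individuals with chronic" stroke are randomized to two groups, stratified by baseline function and age.

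**The concern.** A person's quality-of-life score at entry feeds into that person's QALY total twice: as the first point of the curve, and through its correlation with every later score. In a trial of 60, the arms will differ somewhat at entry by chance, and an unadjusted QALY difference carries part of that gap.

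The plan recognises this for the motor outcomes and handles it there. For the Aim 2 primary outcome it leaves the choice open. At stake are the precision of the QALY difference, and with it the ICER, the acceptability curve and the two- and five-year forecasts built on the 6- and 12-month results. Leaving the choice until imbalance has been seen also adds avoidable analytic flexibility.

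**Working it through.** **The plan's own figures.** The documents give no power, standard error or expected gain for QALYs. The only power statement, in Power and Sample Size Justification, concerns the FMA: 0.87 for an effect size of 0.4 with 30 per arm at the 0.05 level. It does not reproduce from the stated 4.25-point difference and SD of 10: 4.25/(10 × √(2/30)) = 1.646, and Φ(1.646 − 1.960) = 0.38. It is reached if 0.4 is read as Cohen's f (d = 0.8): Φ(0.8/0.2582 − 1.960) = 0.87. That is a separate matter and is not used below.

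**Step 1: chance baseline gap (documents only).** With 30 per arm, the standard error of a difference in baseline means is √(2/30) = 0.258 SD, and the 95% range is ±1.96 × 0.258 = ±0.51 SD. If the strata explained 25% of utility variance (assumed), it would be 0.258 × √0.75 = 0.224 SD.

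**Step 2: assumptions for the QALY scale (none in the documents).**
- The QALY is a within-trial area under the curve, with visits at 0, 4, 8, 12 and 26 weeks.
- Utility SD is 0.15–0.25.
- Correlation between visits is r = 0.5–0.8, equal for all pairs; a decaying version follows in Step 4.

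Trapezoid weights w in years are 0.038, 0.077, 0.077, 0.173 and 0.135 (sum 0.5; sum of squares 0.0614).

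**Step 3: central case, SD 0.20, r = 0.7.**
- Slope of QALY on baseline: 0.0385 + 0.7 × (0.5 − 0.0385) = 0.3615.
- One-standard-error baseline gap: 0.20 × 0.2582 = 0.0516. Resulting QALY shift: 0.3615 × 0.0516 = 0.0187.
- Variance of one person's QALY: 0.04 × (0.7 × 0.25 + 0.3 × 0.0614) = 0.00774.
- Unadjusted standard error: √(2 × 0.00774/30) = 0.0227.
- Correlation of baseline with QALY: 0.3615 × 0.20/√0.00774 = 0.82.
- Adjusted standard error: 0.0227 × √(1 − 0.822²) = 0.0129, a cut of 43%.

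Estimating the baseline slope costs about 1 + 1/(60 − 4) = 1.018 in variance, under 1% in standard error, and is ignored here.

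Over SD 0.15–0.25 and r = 0.5–0.8, the one-standard-error shift runs from 0.010 to 0.026 QALY.

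**Step 4: range of the precision gain.** The percentage cut does not depend on the utility SD. In the decaying pattern, the correlation at t weeks is the four-week value raised to t/4. In the last column, the strata explain 25% of utility variance at every visit (0.25 taken off every entry of the correlation matrix) and are in both analyses.

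| Correlation pattern | Cut in standard error | Equivalent sample size | Cut, strata in both |
|---|---|---|---|
| Equal, 0.5 | 27% | 1.9 times | 16% |
| Equal, 0.7 | 43% | 3.1 times | 34% |
| Equal, 0.8 | 53% | 4.6 times | 46% |
| Decaying, 0.7 per 4 weeks | 17% | 1.4 times | 6% |
| Decaying, 0.8 per 4 weeks | 26% | 1.8 times | 15% |
| Decaying, 0.9 per 4 weeks | 42% | 3.0 times | 33% |

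**Step 5: cross-check.** A coarser grid of 0, 8 and 26 weeks, with SD 0.20 and r = 0.7, gives 0.0234 falling to 0.0132, also a cut of about 43–44%.

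**The case against.** The strongest reply is that the plan is silent rather than committed to an unadjusted analysis. The sentence on model inputs concerns outcome probabilities, which are not utilities, and nothing says that raw arm means go into the model. The covariate clause stands outside the Aim 1 paragraph and could be stretched to QALYs. This stands: a reader might infer that the plan has decided against adjustment, and the documents do not support that. What remains is that no adjustment is prespecified. The clause does not close the gap, because it is optional, depends on the observed data, omits quality of life and has no link to the QALY analysis.

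Second, Aim 2 is a decision-analytic model, and its rationale names absolute change in motor function among the variables driving the ICER. A model that starts both arms from a common cohort, or works from changes, would not pass on the baseline gap as calculated above. This also stands, and it makes the QALY-scale figures illustrative.

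Third, randomization makes the expected gap zero, and a correct unadjusted standard error already includes chance imbalance. A reader might infer systematic bias; that would be wrong. Lost precision and error given the observed gap are largely one problem seen twice, and a well-built probabilistic analysis would display the extra uncertainty. Displaying it is still worse than removing it with data already collected.

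Fourth, a reader might infer that the chance gap rivals the treatment effect. The documents give no expected QALY gain with which to judge this. If a sustained utility gain of 0.03, 0.05 or 0.10 is reached linearly by week 8, it is worth that gain × (0.5 − 0.5 × 8/52) = 0.013, 0.021 or 0.042 QALY. In the central case, the chance shift is at least that large in either direction with probability about 50%, 26% or 2%. With SD 0.10–0.25 and r 0.5–0.85 on the coarser grid, the probabilities run from 0% to 65%. The comparison depends almost wholly on what is assumed.

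**Conclusion.** The omission is real and can be read directly from the documents: baseline adjustment is specified for three motor outcomes and not for the QALYs behind the Aim 2 primary ICER. Confidence in that is high. The 0.26 SD standard error of the chance baseline gap follows from the sample size alone, before any trimming by stratification.

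The size of the benefit is illustrative. It rests on an area-under-the-curve QALY and on assumed correlations: about 27–53% off the standard error with equal correlation of 0.5–0.8, or 17–42% with decay. If the strata explain a quarter of utility variance, these become 16–46% and 6–33%. Every case favours adjustment, though the last can be modest.

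The documents do not support the claims that the plan rejects adjustment, that the QALY comparison is systematically biased, or that a chance gap is known to match the treatment effect. Nor does the QALY difference settle all of Aim 2: the ICER also depends on costs, and recurrence, readmission, mortality, depression, return to work and participation are analysed as well. The change should be made because it improves the primary economic estimate at almost no cost.

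**What to change.** In Data analysis, Cost-Effectiveness Analysis (Aim 2), state that:

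1. 6- and 12-month QALYs will be compared by regression on group, baseline utility and the randomization strata (baseline function and age), whatever imbalance is observed.
2. The adjusted estimates and their covariance will feed the decision model, the probabilistic sensitivity analysis and the acceptability curve.

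The cost is a few sentences of plan text and a few degrees of freedom out of 60 participants. No new visit, instrument or participant is needed. The wording presupposes a named method for turning the SIS or PROMIS 29 into a utility. The documents name none; that choice is a separate matter, but it has to be made before this analysis can be run.

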### **Aim 2: To determine the cost-effectiveness of pairing aerobic exercise with UE repetitive task practice compared to UE repetitive task practice only to facilitate motor recovery following stroke.**

**Rationale:** Stroke-related disability has a significant economic impact on patients, their families, and society as a whole. Novel approaches that improve recovery, overall health, and optimize resources including indirect costs borne by patients, are necessary to maximize the value of stroke rehabilitation. The proposed intervention is hypothesized to increase value by providing an approach that improves outcomes and is delivered in a manner that is less resource intensive. As preliminary data suggest that outcomes were superior with the combined approach of AE+RTP, a cost-effectiveness analysis using a decision analytic model is proposed to address the clinical and economic differences between the two proposed interventions. The model will address: cost-effectiveness in the short and long term; cost-effectiveness from the healthcare provider and patient perspective, and identifying specific social determinants of health that impact the cost-effectiveness of the interventions. A tornado diagram from a study investigating the cost-effectiveness of primary stroke centers is presented in Figure 3. This diagram is included as a sample output, as it depicts one-way sensitivity analyses for variables which influence the ICER, and the magnitude and range of their contributions. The modeling techniques I learn as part of my training will produce comparable visualizations, demonstrating the impact of variables contributing to the ICER (such as absolute change in motor function, level of disability, change in cardiovascular function, employment, mortality, etc) in a quantitative manner.

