**Outcomes:** The primary outcome will be the ICER (change in dollars and QALY's between interventions) at six months, while the secondary outcome will analyze the ICER on a subset of participants at 12 months.. The ICER is an analytic tool in which costs and effects of two or more interventions are calculated and presented in a ratio of incremental cost versus effect. Quality metrics will be derived from the Stroke Impact Scale (SIS) and PROMIS 29. Additional analyses will be conducted for the stroke recurrence, readmission, mortality, change in depression, return to work, and participation/compliance. All analyses will be conducted from the perspective of the healthcare sector and society, per recommendations by the second panel on cost-effectiveness in health and medicine. Based on 6- and 12-month ICER outcomes, forecasting will be used to predict the optimal intervention at 2 and 5 years. [name] has used these analytical approaches extensively and will oversee all aspects of the cost-effectiveness analyses.

**Expected results and interpretation:** Reimbursement for medical and rehabilitation services in the US is shifting from a model of volume-based to value-based. A result is the advent of Accountable Care Organizations (ACO), in which insurers partner with healthcare organizations to manage population health, and reward them for optimization of cost and quality. Based on preliminary data, it is hypothesized that AE+RTP will be optimal in terms of the ICER at six and 12 months. Demonstrating value, by improving outcomes and reducing cost, is novel and would serve to engage ACO's in terms of potential adoption of the proposed rehabilitation approach. It is also hypothesized that the ICER will improve for the optimal strategy as the time frame is increased. Given the significant potential for AE to impact overall cardiovascular health, disability, morbidity, and mortality, it is hypothesized that the ICER will be most improved from the societal perspective, favoring AE+RTP.

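### A medical price index is applied to all costs, so indirect costs in the societal ICER may be mis-scaled

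*Combined protocol and SAP*

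**What the plan says.** In the Combined protocol and SAP, the costing rule is in Data Variables, in the paragraph on cost-effectiveness variables for Aim 2: "All costs will be adjusted to the same base year using the Medical Component of the Consumer Price Index". It has no exception, and no other index is named. The sentence before it reads: "Labor prices will be sourced from the Bureau of Labor and Statistics using US averages". No price year is given for those rates.

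The same paragraph plans more than medical costs. Of the demographic, employment and support data and the questionnaires, it says: "These measures will ensure the accurate calculation of quality indices and indirect costs". The Aim 2 rationale likewise speaks of approaches that "optimize resources including indirect costs borne by patients".

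On perspective, the Aim 2 outcomes paragraph says "All analyses will be conducted from the perspective of the healthcare sector and society". The Data analysis section promises an "incremental cost-effectiveness ratio between the interventions from two perspectives: healthcare sector and society". Earlier in that same Data analysis paragraph, however, stands: "A hospital/payer perspective will be adopted and include all relevant costs and outcomes".

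**The concern.** Lost work and similar indirect costs are not medical goods, and their prices need not move with medical prices. If such a cost arises in one year and is carried to the base year with the medical index, it is scaled by the wrong factor whenever the two price series differ.

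The indirect costs are also what separates the societal result from the healthcare-sector result. The plan puts weight on that contrast: "it is hypothesized that the ICER will be most improved from the societal perspective, favoring AE+RTP". The six-month ICER is the primary outcome of Aim 2, and the Limitations and Future Directions paragraph gives the study a 5-year span, so costs can be several years from a common base year.

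**Working it through.** **Is there a figure to reproduce?** No. The documents state no ICER, cost amount, base year, inflation rate or non-medical share. What follows shows a range under assumptions.

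**Formula.** Let m be the annual growth of the medical index, g the annual growth of the index suited to non-medical costs, t the years adjusted, and s the non-medical share of the incremental cost.

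- Error on the non-medical component: r = ((1+m)/(1+g))^t − 1
- Relative error in the societal incremental cost: s × r. With the QALY difference unchanged, this is also the relative error in the ICER.

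**Inputs.** From the documents: t can be at most about 5 years. Assumed: g = 2% a year, m − g from −2 to +3 points, s from 0 to 1.

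**Values of r (error on the non-medical component):**

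| m − g | t = 1 | t = 2.5 | t = 5 |
|---|---|---|---|
| −2 points | −1.96% | −4.83% | −9.43% |
| 0 | 0 | 0 | 0 |
| +1 point | 0.98% | 2.47% | 5.00% |
| +2 points | 1.96% | 4.97% | 10.20% |
| +3 points | 2.94% | 7.52% | 15.60% |

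With g = 0 the formula reduces to (1+d)^t − 1, where d is the index gap. At d = 0.01 and t = 2 this is 1.020 − 1 = 2.0%. At d = 0.03 and t = 5 it is 1.159 − 1 = 15.9%. Hence the range of about 2% to 16%.

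**From component to ICER.** At s = 0.5 and a gap of +2 points, the shift is 0.98%, 2.49% and 5.10% at 1, 2.5 and 5 years. At s = 0.25, +3 points and 5 years it is 0.25 × 15.60% = 3.90%.

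**A more typical cost age.** The Recruitment and Sample paragraph reports 30 participants in 21 months. At that pace 60 take about 42 months, and six months of follow-up brings the total to 48. Assume even enrolment, costs spread evenly over each participant's six months, and a base year at the end of collection. The mean cost date is then 21 + 3 = 24 months, so costs are on average 48 − 24 = 24 months old. At 2 years, gaps of 1 to 3 points give 1.01² − 1 = 2.0% to 1.03² − 1 = 6.1% of the component, or about 1% to 3% of the incremental cost at s = 0.5.

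**Where it could be larger.** If the medical and non-medical increments have opposite signs and nearly cancel, s lies outside 0 to 1. Two invented examples, with a gap of +2 points over 5 years (factor 1.1020):

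- Medical −1000, non-medical +800: the net should be −200 but becomes −1000 + 881.6 = about −118.
- Medical −1000, non-medical +950: the net should be −50 but becomes −1000 + 1046.9 = about +47, a change of sign.

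**Where it vanishes.** The error is zero if the two indices move together, if the non-medical increment is zero, or if non-medical costs are priced directly in the base year.

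**The case against.** The strongest reply is that the rule may do no harm. A cost already in base-year prices is not changed by adjustment to the base year. Labor rates could be taken for that year, and nothing in the plan forbids valuing lost work the same way. This stands as a reason not to claim that an error will occur. It does not clear the rule: the plan does not say that costs will be priced this way, and the stated instruction covers every cost.

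Second, a hospital/payer analysis would make a medical index largely unobjectionable. But the same Data analysis paragraph goes on to require the societal result, so the sentence is a contradiction to resolve and not a defence.

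Third, the Experimental Overview gives both arms the same contact time (36 hours over 8 weeks, three sessions a week). Intervention-related patient time and travel should therefore be about equal between arms, and neither is listed as a cost item. This stands: only arm differences in items such as work loss or informal help could carry the error.

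Fourth, deterministic and probabilistic sensitivity analyses are planned. They could absorb the question, but the price index is not named among their inputs.

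A reader might infer that the mismatch tilts the result toward the stated hypothesis for AE+RTP. The documents do not support this. It would need medical prices to outrun the suitable index and AE+RTP to save indirect costs, and neither is established. With concurrent randomized enrolment the same factor applies to both arms in a given year. It stretches or shrinks whatever non-medical difference exists and does not favor an arm by construction.

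**Conclusion.** Wrong as written, minor in size. The plan sets a rule that scales all costs with a medical index while also planning indirect costs and a societal ICER. Indirect costs not already in base-year prices would be scaled by an unsuitable index, so the societal ICER may be mis-scaled. The healthcare-sector ICER is not affected through this route.

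It would go too far to say that the societal ICER is misstated, or to quote 16% as an error in the ICER. The 2% to 16% applies to the non-medical component only, and its upper end needs a 3-point gap with every affected cost five years old. On the incremental cost the shift is usually a few percent. It is larger only if increments nearly cancel, and its sign reverses if medical prices grow more slowly. All of this rests on assumed index gaps, cost ages and non-medical shares, since the documents give none of them.

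**What to change.** In the costing paragraph of Data Variables:

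- State the base year.
- Value recorded resource quantities, including personnel time, at unit prices of that year, with labor rates taken for the same year.
- Where a price exists only for another year, use the medical index for health-care items only. Use a general consumer price or wage index for productivity and any other non-medical cost that the trial collects.

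In Data analysis, reconcile the hospital/payer sentence with the healthcare-sector and societal statements. The index choice can be added as one input to the planned deterministic sensitivity analysis.

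The cost is a sentence or two of text. No new participant data are needed, because the change covers only costs the trial already collects. It should be made before costs are analyzed, so that the index is not chosen with results in view.
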